The text-messaging system may make up to a total of 3 attempts until the participant responds with a BP. Some messages for that week may then be tailored on that BP recording.

Please note this will be the only Reach Out research specified outbound message that will be permissible from the participants to the research team. Otherwise, messages sent by the participant will trigger an automated response saying that the response is automated and that for emergencies, the participant should call 911. Participants who have a BP >180/120 will be sent an automated message telling them to call their doctor right away, as they likely need more or different medication, and if they have symptoms such as chest pain, weakness, difficulty talking, or confusion to call 911.. Additionally, if a message is sent to the system that doesn't make sense in the context of a BP reading, an automated error message will be sent back for them to resubmit their BP in the previously taught method.

Participants will have the option to modulate their own reminder frequency by texting prompts to either receive daily BP message reminders, weekly message reminders, or setting them back to where they were assigned at baseline.

6.1.3 **Facilitated primary care provider appointment scheduling and transportation**

Recognizing the importance of primary care provider visits and transportation, Reach Out will facilitate primary care provider appointment scheduling and transportation. Participants will be randomized to receive either facilitated scheduling and transportation, or passive reminders.

Participants randomized to the facilitated group will be able to schedule appointments with their primary care provider via phone call or text capability, which may be facilitated by the research team depending on the capability of our scheduling system. If a provider office indicates that they require proof of permission from participant regarding the ability to schedule appointments

on their behalf, REACH OUT may provide that to them for their files, or complete the office's specific permission forms (Appendix H).

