2.3. Description of participants

Purpose: To describe the patient population by intervention group.

Methods/Approach: Construct “table 1” describing the baseline characteristics of each intervention group including:

- Demographic characteristics
- Baseline medical history, Tobacco/Alcohol Information, Insurance Status, Transportation Status, Social Cognitive Theory Measures, medication history, medication adherence
- Baseline values of primary and/or secondary outcome variables: BP, PCP Attendance

Means and standard deviations will describe continuous variables, frequencies and counts will describe categorical variables. Significance testing of baseline differences between groups will not be performed based on statistical and CONSORT recommendations.¹⁻²

Intervention Exposure: Participants receiving daily BP monitoring or healthy behavior text messaging can choose to “snooze” (stop texts for 2 weeks) or de-escalate their treatment “weekly” (stop healthy behavior text messages, move to weekly BP monitoring). Participants with weekly BP monitoring can choose to “snooze” treatment (stop texts for 2 weeks) or escalate their treatment “daily” (daily BP monitoring no change to healthy behavior text messaging). The number and percentage of participants who “snooze” BP monitoring and healthy behavior texts, both daily and weekly, will be reported separately. The number and percentage of participants who choose to de-escalate from daily BP monitoring and healthy behavior texts will be reported separately as well the number and percentage who escalate their treatment. The proportion of all possible BP monitoring texts (either daily or weekly) completed for each subject will be calculated and the proportion and 95% confidence interval will be reported by intervention group.

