2.5. Secondary analyses

Purpose:

1. To evaluate interactions of treatments in the change of BP over 12 months.
2. To evaluate the pattern of change of BP over time.
3. To evaluate time from ED visit to arrival at first primary care visit (in days).
4. To evaluate attendance at two or more primary care visits within 12 months of randomization.

Methods/Approach: The following secondary analyses will be presented:

(a) Other analysis approaches on the primary measurement:

Additional analyses will include all the two-way interactions of the three intervention components (only considering interactions where at least one of the factors in the interaction demonstrates a sufficiently large main effect) added to the primary model in Section 2.4. Interactions between treatments will be assessed at $p=0.2$.

Since BP levels are captured at least weekly, we will also model BP (captured by text and in person visits) over time using a mixed effects model to see the pattern of blood pressure levels over time. The outcome of this longitudinal model will be BP levels over time (transformed if necessary), where the number of BP levels per person can vary. The fixed effects of the model include: the 3 main effects binary coded treatment predictors and the 3 stratification variables as specified in the primary analysis model. A random slope for a continuous time variable measured in days from randomization and a random intercept to allow subject specific heterogeneity in baseline BP and BP trajectories over time. We will assume compound symmetry for the covariance matrix but assess the appropriateness of this assumption using AIC and BIC compared to unstructured and autoregressive structures. We will also assess the significance of two-way interactions of treatments (only where at least one of the factors demonstrates a sufficiently large main effect) in this model at the 0.2 level. Mixed effects models are robust to data missing at random.

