As a sensitivity analysis, similar to a per protocol analysis, we will assess the effect of using group variables that may change from week to week as opposed to the given randomized treatment variable that stays fixed over the treatment period (intent to treat group). For example, if someone de-escalates from daily to weekly monitoring in a particular week, we can capture this in a longitudinal model by allowing their group variable to change from daily to weekly in that week. This will allow us to connect the BP measurement with the group assignment for that week, thus we will use all BP measurements. Otherwise, the mixed model construction will be the same as detailed in the paragraph above.

(b) Other outcomes (secondary outcomes):

- To evaluate time from ED visit to arrival at first primary care visit (in days)

- Unadjusted survival distributions for receiving provider scheduling and transportation versus not and for all 8 intervention arms will be estimated and plotted by the Kaplan-Meier method and compared using the log-rank test.
- Cox proportional hazards regression model will assess the time from ED visit to arrival at the first primary care visit where all of those who do not have a recorded PCP visit will be censored at the time of last follow-up (last communication/text) or 12 months. The main predictor of interest for these models is assignment to the active primary care provider scheduling and transportation arm (50% of all subjects randomized in the trial), while adjusting for the assignment into other groups (healthy behavior text messages and prompted BP self-monitoring). We will control for age, sex, previous use of antihypertensives, and race. The interactions of these baseline variables will be assessed. The proportionality assumption will be assessed via Schoenfeld residuals by evidence of a non-zero slope in a generalized linear regression of the scaled residuals by time and goodness of fit will be assessed by the Grambsch-Therneau test.
- To evaluate attendance at two or more primary care visits within 12 months of randomization.

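### The longitudinal BP models have no fixed time effect, so part of any BP change shared by all arms leaks into the component coefficients

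*SAP*

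**What the plan says.** SAP 2.5(a) sets out two mixed models for BP level over the year, using texted and in-person readings.

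- **Assigned-group model.** "The fixed effects of the model include: the 3 main effects binary coded treatment predictors and the 3 stratification variables". Time is placed in the random part: "A random slope for a continuous time variable measured in days from randomization and a random intercept".
- **Week-by-week model.** This is a sensitivity analysis likened to per protocol. It replaces the fixed assignment by "allowing their group variable to change from daily to weekly in that week", uses all readings, and then states: "Otherwise, the mixed model construction will be the same as detailed in the paragraph above".

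No fixed effect of time is named in either model.

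Switching is allowed in both directions, but not equally for each component. SAP 2.3 (Intervention Exposure) defines the weekly option as "stop healthy behavior text messages, move to weekly BP monitoring", so it can remove texts as well as daily prompts. The daily option raises monitoring frequency and leaves texts as they were. SAP 2.3 will report those who step down and "as well the number and percentage who escalate their treatment". Protocol 6.1.2 agrees: "Participants will have the option to modulate their own reminder frequency by texting prompts to either receive daily BP message reminders", or weekly ones, or a return to the assigned frequency. None of the documents gives an expected switching rate or a variance for BP readings.

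**The concern.** Everyone starts at the assigned level, so a first switch always follows weeks at that level. In the week-by-week model a switched component's coefficient is therefore partly a later-versus-earlier comparison within the same person. If BP falls in all arms, some of that fall is attributed to whatever level people move to. Switching need not be prompted by BP for this to happen.

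The plan gives reasons to expect a shared fall. Randomisation requires a high self-reported reading (Protocol 5.3.4), which invites regression to the mean. There is no untreated arm, because prompted monitoring is considered efficacious (Protocol 6.1). The rule for a null trial looks for a fall in arm 1, the lowest-intensity arm (SAP 1).

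The week-by-week model is the plan's as-received check on the intention-to-treat result. A bias near the minimal effect could make it contradict a correct primary result. SAP 2.6 also repeats the 2.5(a) modelling within baseline-BP tertiles, where regression to the mean would differ between strata.

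**Working it through.** The plan gives no figure for these models, so there is nothing to reproduce. The outcome is BP level, so a positive coefficient means the component looks harmful.

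**1. Model as written.** BP_it = b0 + b1·HBtexts_it + b2·HighBPmonitor_it + b3·PCPfacilitated_i + strata + u0_i + u1_i·day + e_it, with u1 having mean zero. In the assigned-group model the codes do not vary with t.

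**2. Yardstick.** Protocol 9.3 gives a standardized effect of 0.35 and an SD of 2.8: 0.35 × 2.8 = 0.98, about 1 mm Hg. Alpha for main effects is 0.10 (SAP 2.4).

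**3. Assigned-group model, no switching (closed form).** Take a shared linear change s per year, n readings spread evenly over the year, residual variance σ², fitted slope variance τ², and uncorrelated random effects. The fitted arm level is then displaced by s × t̄ × λ, where λ = (σ²/S)/(τ² + σ²/S), S = n/12 and t̄ = 0.5. Arms with fewer readings have larger λ.

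- Inputs: s = −10, σ = 10 and true slope SD 5 (all assumed); 47% response to prompts (pilot, Protocol 2.2.1). The zero-mean slope absorbs the trend as variance, so τ² ≈ 5² + 10² = 125.
- Weekly: n = 52 × 0.47 = 24.4; S = 2.04; σ²/S = 49.1; λ = 49.1/174.1 = 0.282; displacement −5 × 0.282 = −1.41.
- Daily: n = 364 × 0.47 = 171; S = 14.26; σ²/S = 7.01; λ = 7.01/132.0 = 0.053; displacement −5 × 0.053 = −0.27.
- Daily minus weekly: −0.27 + 1.41 = **+1.14 mm Hg** with no true effect.

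Simulation of this case also gave +1.14 (Monte Carlo SE 0.21), and −0.04 with fixed time. With equal reading rates it gave −0.01. Other assumptions gave +0.73, again removed by fixed time.

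**4. Week-by-week model, monitoring component.** Simulation with N = 480, no true effect, switch week random and unrelated to BP, switches permanent. Assumed: between-person SD 12, slope SD 5 mm Hg/year, residual SD 10, linear shared fall of 10 mm Hg, 47% response, 40 runs per row.

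| Switching | Readings per week | Bias as written (SE) | Rejected at 0.10 | Bias with fixed linear time |
|---|---|---|---|---|
| 30% down | up to 7 vs 1 | +1.36 (0.50) | 93% | −0.03 |
| 30% down | 1 for all | +1.88 (0.64) | 88% | +0.13 |
| 10% down | 1 for all | +1.25 (0.89) | 35% | +0.25 |
| 30% up | 1 for all | −1.81 (0.64) | 85% | +0.01 |
| 30% up | up to 7 vs 1 | −0.74 (0.51) | 42% | +0.09 |
| 30% down and 30% up | 1 for all | +0.05 (0.50) | 12% | −0.01 |
| 30% down, no shared fall | 1 for all | −0.12 (0.58) | 5% | −0.09 |

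Rough check: rejection ≈ Φ(|bias|/SE − 1.645) + Φ(−|bias|/SE − 1.645). For 1.36/0.50 = 2.72 this gives 86%; for 0.74/0.51 = 1.45, 42%. With only 40 runs, the agreement is adequate.

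**5. How much leaks.** 1.36/10 = 14% and 1.88/10 = 19%. In the setting of the first row, a 5 mm Hg fall gave +1.11 (22%) and a 20 mm Hg fall +1.24 (6%). The random slope takes up most of a large fall: without it, the first-row bias would be about +4.4.

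**6. Smaller fall.** With 30% switching down and a 4 mm Hg fall (slope SD 6, half the participants stopping texting early, 400 runs), bias was +0.8 to +0.9 for a linear fall, with 26% rejection at N = 240 and 40% at N = 480. For a fall mostly in the first weeks it was +0.6 to +0.65, with 20% and 28%. Another set at N = 480 gave +0.5 to +0.7 (20–24%) for 4 mm Hg and +0.9 to +1.1 (38–46%) for 10 mm Hg.

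**7. Texts and monitoring together.** With 30% switching each way under the SAP 2.3 rule (N = 480, 100 runs), monitoring largely cancels but texts do not:

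- 4 mm Hg fall: texts +0.86 (41% rejected); monitoring −0.12 (11%).
- 10 mm Hg fall: texts +1.26 (66%); monitoring −0.19 (9%).
- Monthly fixed time: both biases about 0, rejection 7–10%.

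A further run at 10 mm Hg gave texts +1.5 (85%). Temporary switches with return to the assigned level cut the texts bias to about +0.24.

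**The case against.** The strongest reply is that the SAP's list of fixed effects may not be exhaustive. It names no intercept either. A model meant to show the pattern of BP over time, with subject-specific trajectories, would ordinarily have a mean trajectory, so a fixed time term may simply have been left unwritten. That is possible, but the text places time explicitly in the random part. An analyst who follows it literally gets the biased model, and two analysts could report different results.

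Other points stand and limit the claim. Switches may be temporary: Protocol 6.1.2 allows a return to the assigned frequency, and a snooze lasts two weeks (Appendix E). Permanent switching is the unfavourable case. The variances, switching rates and shared fall are all assumed. In particular, the 3–4 mm Hg in Protocol 9.3 is the improvement wanted from the chosen regimen, not a forecast of a fall common to all arms, so 4 mm Hg is only illustrative. No decision rule is attached to the sensitivity analysis, and the planned plots of mean BP over time (SAP 2.4) would show a shared fall.

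A reader might also infer that the whole shared fall is credited to the lower dose. The documents do not support this: the random slope absorbs most of the fall, and escalation is allowed, which credits the leak to the higher dose.

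**Conclusion.** The concern holds for both longitudinal models in SAP 2.5(a). As written, part of any BP change shared by all arms enters the component coefficients. In the week-by-week model this pushes healthy behavior texts toward looking harmful. For monitoring frequency the sign follows whichever switching predominates, and balanced switching largely cancels it. It would be tempting to treat the assigned-group model as safe because randomised codes are balanced over time, but unequal reading frequency can bias its monitoring coefficient with no switching at all.

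Under the assumed variances and 30% permanent de-escalation unrelated to BP, the bias is about 0.5 to 0.9 mm Hg for a 4 mm Hg shared fall and 0.9 to 1.9 mm Hg for a 10 mm Hg fall, comparable with the 1 mm Hg minimal effect. With no shared fall, rejection is near nominal.

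A reader might infer that component selection is compromised. It is not: the primary analysis (SAP 2.4) uses one 12-month change score per participant with randomised codes, and this mechanism does not reach it. The change should be made, but it concerns secondary and sensitivity results only.

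**What to change.** In SAP 2.5(a), add to the assigned-group longitudinal model a fixed effect of time since randomisation, common to all arms, in flexible form (monthly categories or a spline). Keep the random intercept and slope, and state that the week-by-week model carries the same term. If the aim is to compare trajectories between levels, say whether time-by-component terms will be added.

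A flexible form is preferable to a straight line: with an early fall, a linear term left a bias of about −0.2 to −0.3 mm Hg.

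The cost is one sentence and a few degrees of freedom, with no new data. Standard errors did not rise materially in the simulations (0.46 against 0.50, and 0.59 against 0.64, in the first two rows of the table). Fixed time does not cure self-selection: participants choose when to switch, and that remains a limitation of the week-by-week analysis to be stated when it is reported.

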Text messages will be both tailored and targeted. Tailoring and targeting are health behavior strategies to increase the personal relevance and therefore the efficacy of behavioral interventions. Targeting refers to the creation of materials focused on shared characteristics of a group of people. In contrast, tailoring refers to materials focused on characteristics of individuals. Studies have shown that tailored and targeted communications are more effective than generic messages. The messages address the most important lifestyle interventions to reduce BP such as, salt reduction, increased fruit and vegetable intake, and increased physical activity. Our team, partnering with the community, created the content for these text messages based on social cognitive theory. Appended are generic, targeted, and tailored text messages. Based on community and hospital feedback, additional text messages may be added, but they will be in the same participant and style of the appended messages.

In addition to these generic health messages, tailored and targeted text messages-based on whether the participant takes an antihypertensive medication, medication adherence level, self-efficacy level, and has a primary care physician will be used. For example, for participants taking

antihypertensive medications, text messages will also address medication adherences (e.g., pill boxes, schedules, etc.).

6.1.2 **Prompted BP self-monitoring**

All participants will have received a BP self-monitoring device at enrollment in the ED, and training for use and text-message response formatting. Participants will be randomized into either a high intensity or low intensity.

- The high intensity group will receive message reminders to check and text their BP back daily
- The low intensity group will be asked to check and text it weekly

By texting their BP, participants have a record of their BPs that they can bring to their primary care provider appointments. They may also be able to prompt the text messaging system to acquire a list of their self-reported blood pressures from the text messaging system. Participants will receive a monthly picture graph of their self-reported blood pressures for feedback. Our platform will allow the participants to provide preferences regarding the time of day for the BP reminders, and the ability to adjust these as needed.

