Incentive	X											X						X	
Cognitive screen	X																		
ED Measured BPs	X																		
Competence w/BP cuff	X					X													
Competence with text messaging	X					X													
ASSESSMENTS:																			
Contact Information	X											X						X	
Demographics	X																		
Medical History	X																		
Tobacco/ Alcohol	X																		
Insurance Status	X																		
Transportation	X																		
SCT measures	X											X						X	
Self- efficacy modified						X	X	X	X	X		X	X	X	X	X	X		
SCT modified	X											X						X	
Self- reported BP measurement		X	X	X															
Study taken BP measurement	X											X						X	
PCP:																			
PCP	X											X						X	
First PCP visit time												X						X	
PCP attendance	X					X	X	X	X	X	X	X	X	X	X	X	X	X	

Reach Out ED
Version 14.0
1 August 2022

BP medication adherence will be assessed using several different methods: 1) Hill-Bone and one-question modified Hill-Bone question; 2) pharmacy and provider notes; 3) text participants to message pictures of their medication prior to the 6 and 12 month follow-ups. We will also ask participants to bring their medication to the 6 and 12 month follow-ups. For participants that have not done either, they will be reminded at the follow-up appointments, and texted once more afterwards. In an attempt to further monitor medication adherence, we will look for medication fill rates within the Hurley EHR, and Hamilton pharmacy records, and if there are linkages to commercial pharmacy, we will scan electronic record to assess. We will evaluate the impact of the interventions, and a brief survey regarding participant feedback on the specific intervention components they received (will be added in a future amendment).

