Sample Size: We plan to enroll approximately 960 patients into the eligibility phase. From this group, we estimate that 480 subjects will report qualifying BPs and will be randomized to one of the eight intervention arms. We anticipate 240 subjects will fully complete the 12 month, in person follow up visit. For 80% power to detect the smallest main expected effect of 0.35 based on the Collins method of a 3-factor experiment analyzed using a second order model (i.e. main effects and 2-way interactions), we require 196 subjects. Assuming 480 randomized subjects and allowing an additional 50% loss to follow up after the eligibility phase, we expect at

least 240 subjects, exceeding 80% power with an alpha level of 0.10 (inflated to reduce likelihood of dismissing active components with modest BP reducing effect) – we used the FactorialPowerPlan SAS macro to calculate power. For the secondary analyses, considering an alpha of 0.05 and a baseline proportion attending 2 or more primary care provider visits within one year of 40%, with a total sample size of 240 evenly distributed between the active appointment scheduling and passive appointment, we have 87% power to detect an increase to 60% attending 2 or more visits. The time to event analysis (considering an alpha of 0.05, power of 99%, and 240 subjects enrolled over 720 days, followed for 30 days) can detect a change from 20% of subjects in the non-facilitated group to 20.4% of subjects in the facilitated group.

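### The Aim 2 Cox and logistic models omit baseline primary care status and attendance, which the trial collects; the tests stay valid, but some power is left unused

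*SAP*

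**What the plan says.** SAP 2.5(b) gives the Cox model for time from ED visit to first primary care visit and the logistic model for two or more visits within 12 months the same structure. The predictor of interest is facilitated scheduling and transportation, "while adjusting for the assignment into other groups (healthy behavior text messages and prompted BP self-monitoring"). The baseline covariates follow: "We will control for age, sex, previous use of antihypertensives, and race". Protocol 9.1 adjusts Aim 2 only for the other components.

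The baseline information exists:

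- The protocol's schedule of measures (section 7) has a row for PCP and a row for "PCP attendance", each marked at baseline.
- Protocol 6.1.1 tailors messages on, among other things, "self-efficacy level, and has a primary care physician will be used", and Protocol 5.3 says that tailoring data are collected at baseline.
- SAP 2.3 lists "Baseline values of primary and/or secondary outcome variables: BP, PCP Attendance" for the descriptive baseline table.

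Randomisation is stratified on age, sex and antihypertensive use only, and SAP 2.6 does not use primary care status as a subgroup factor. So the baseline primary care variables enter no model in either document.

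On power, SAP section 1 works with "considering an alpha of 0.05 and a baseline proportion attending 2 or more primary care provider visits within one year of 40" per cent, "with a total sample size of 240 evenly distributed between the active appointment scheduling and passive appointment", and concludes that "we have 87% power to detect an increase to 60% attending 2 or more visits".

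**The concern.** Prior attendance is close to a baseline value of the Aim 2 outcomes, and having a provider plausibly bears on both endpoints. Under Protocol 6.1.3, a participant without a provider must first have care established at a community health centre, while others book with their existing provider. If these variables are prognostic, leaving them out of a logistic or Cox model lowers the power of the facilitation test. It also leaves any chance difference between the facilitated and non-facilitated groups unadjusted. Aim 2 is tested at alpha 0.05, not the 0.10 used for the primary main effects, and Protocol 9.3 reports retention below expectation, so efficiency has some value here.

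**Working it through.** **Inputs from the documents.** Control rate 40%, facilitated rate 60%, 120 per group, alpha 0.05 (taken as two-sided). The only figure on lacking a provider is 15%, from the church pilot in Protocol 2.2.1, which is a different population. It suggests 85% prevalence as one end of a range.

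**Assumptions (not in the documents).** Provider prevalence 50%, 70% or 85%; covariate odds ratio 2 to 10 (logistic); covariate hazard ratio 1.5 to 5, the facilitation hazard ratio and the 12-month visit rate (Cox).

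**1. Reproduce the stated 87%.**
- Pooled two-proportion test: [0.20 − 1.96·√(2·0.5·0.5/120)] / √(2·0.24/120) = (0.2000 − 0.1265)/0.0632 = 1.162, so power is 87.7%.
- Logit Wald test: ln(2.25) = 0.811; SE = √(2/(120·0.24)) = 0.2635; z = 3.077; power = Φ(3.077 − 1.96) = 86.8%.

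The stated figure reproduces with no baseline covariate in the calculation.

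**2. Logistic model with one binary covariate.** Hold the marginal rates at 40% and 60%. Solve prev·expit(a + ln OR) + (1 − prev)·expit(a) = 0.40 for a, and the same equation with 0.60 for a + t. Take the SE of t from the information matrix; power is Φ(t/SE − 1.96).

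Example, prevalence 85% and OR 5: a = −1.826, so control rates are 13.9% without and 44.6% with a provider (0.15·13.9 + 0.85·44.6 = 40.0). t = 0.866, so the conditional OR is 2.38; SE = 0.2735; z = 3.168; power 88.6%. The SE rises slightly (0.2635 to 0.2735), but the conditional log odds ratio rises more (0.811 to 0.866). That is where the gain comes from.

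| Prevalence | OR 2 | OR 3 | OR 5 | OR 10 |
|---|---|---|---|---|
| 85% | 87.2% | 87.8% | 88.6% | 89.8% |
| 70% | 87.5% | 88.4% | 90.0% | 92.3% |
| 50% | 87.6% | 88.8% | 90.7% | 93.5% |

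The comparator is 86.8% throughout. At OR 1 nothing changes, and no cell falls below the comparator.

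**3. Cox model, by simulation.** N=240, exponential times, censoring at 12 months; power without → with the covariate. With 1,000 runs, the simulation standard error of each power is at most √(0.5·0.5/1000) = 1.6 points.

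| Facilitation HR; visit rate by 12 months | Prevalence | Covariate HR 2 | Covariate HR 3 |
|---|---|---|---|
| 1.45; about 73-78% of all participants | 50% | 65 → 72% | 57 → 71% |
| 1.55; 60% of controls | 50% | 74 → 79% | 70 → 79% |
| 1.55; 60% of controls | 85% | 78 → 80% | 75 → 80% |
| 1.45; 40% of controls | 50% | 47 → 50% | 41 → 47% |
| 1.45; 40% of controls | 85% | 50 → 50% | 46 → 49% |

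If only 20% of controls have a visit, the gain is about 0-2 points. In the HR 1.55 setting, a covariate HR of 1.5 gains about 0-1 point and an HR of 5 gains 8 points (70 → 78%, prevalence 85%) to 24 points (53 → 77%, prevalence 50%).

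**4. Chance imbalance.** Without stratification, the standard deviation of the between-group difference in provider prevalence is √(2·0.85·0.15/120) = 4.6 percentage points at 85%, and √(2·0.5·0.5/120) = 6.5 points at 50%.

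**The case against.** The strongest reply is that this is a preference. Randomisation makes the planned tests valid, covariates are pre-specified, the stated power reproduces without this one, and the endpoints are secondary in a trial that calls itself exploratory. All of that is true. It limits the weight of the point but does not answer it, because the data are already collected and logistic power did not fall in any setting examined.

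Further points stand in part:

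- **Size is assumed.** No document says how prognostic these variables are. At 85% prevalence the logistic gain is only 0.4 points (OR 2), 1.0 (OR 3) or 1.8 (OR 5).
- **The planned model may hold a proxy.** Antihypertensive use is already a covariate. If, say, 70% of those with a provider and 20% of those without use antihypertensives, with OR 2 for use, the added gain at 85% prevalence is 88.2 → 88.9% (OR 3) or 88.5 → 89.8% (OR 5).
- **Definition.** The documents give no coding or look-back window for baseline attendance, and status and attendance overlap.
- **Effect modification.** The separate pathway for people without a provider might change the effect of facilitation. A main-effect covariate does not address that.

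A reader might infer that the planned estimates are biased toward no effect. They are not. The smaller unadjusted odds or hazard ratio reflects non-collapsibility: adding a covariate changes the conditional effect being estimated.

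Nor does Protocol 9.3's claim of 99% power with room for covariates show power to spare. For 20% vs 20.4%, the hazard ratio is ln(0.796)/ln(0.80) = 1.022. With about 48 events (240·0.202), z is about 0.022·√(48/4) = 0.08 and power is about 3%. That statement needs its own correction.

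**Conclusion.** The point holds as a worthwhile, low-cost improvement to the analysis, not as an error that invalidates Aim 2. The omission and the baseline collection are plain in the documents, and the direction of the effect on power is secure if the covariate is prognostic.

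The size is not secure. For two or more visits the gain is about 0.4-2 points for a covariate OR of 2-3, about 2-4 points at 5, and up to about 7 points at 10 with 50% prevalence. For time to first visit it is about 0-7 points at a covariate HR up to 2 and about 3-14 points at 3, shrinking to about 0-2 points if only a fifth of controls have a visit. Confidence is high on the omission and low on the magnitude.

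Two stronger readings go beyond the documents. One is that the 87% figure is wrong or depends on this covariate; it reproduces without it. The other is that the SAP itself names provider status as a baseline value of the outcome; SAP 2.3 names attendance only, and status rests on the protocol's schedule and tailoring text.

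**What to change.** In SAP 2.5(b), add a pre-specified baseline primary care covariate to both the Cox and the logistic model and keep the present covariates. Use provider status (yes/no), and add baseline attendance if it is not redundant with status. State the source, coding, look-back window and handling of missing values, and fix them before any unblinded analysis. Report the odds ratio and hazard ratio as effects conditional on the covariates, as the planned models already do. If the team expects facilitation to work differently for people without a provider, specify that interaction separately.

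The cost is a few lines in the SAP, plus the decision on how baseline attendance is defined. No new data collection is needed, and the sample size does not change.
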